#### Protocol: 3. OBJECTIVES AND PURPOSE

The primary purpose of this Proof of Concept study is to test the hypothesis that TNF inhibition with adalimumab (Humira) in patients with up-regulation of the intra-renal TNF pathway will result in reduction in urinary indicators of TNF pathway activation, specifically urinary MCP1/uCr and TIMP1/uCr levels.

Furthermore, this study is proposed to test the hypothesis that FSGS patients with upregulation of the TNF pathway can be identified through intra-renal gene expression profiling and assay of urinary MCP1/uCr and TIMP1/Cur levels by ELISA.

#### SAP:

Section 1.1 Preface

This proof-of-concept, multi-center, open-label clinical trial addresses the treatment of patients with clinically active FSGS or TR-MCD and urinary biomarkers of intra-renal TNF up-regulation, including urinary monocyte chemoattractant protein 1/urinary creatinine (urinary MCP1/uCr) and urinary tissue inhibitor of metalloproteinase 1/urinary creatinine (urinary TIMP1/uCr).

Section 3.1 Primary Aim and Hypothesis.

The primary purpose of this proof-of-concept study is to test the hypothesis that TNF inhibition with adalimumab (Humira) in patients with up-regulation of the intra-renal TNF pathway results in reduction in urinary indicators of TNF pathway activation, specifically urinary MCP1/uCr or TIMP1/uCr levels.

Hypothesis:

TNF inhibition with adalimumab (Humira) in patients with up-regulation of the intra-renal TNF pathway will result in reduction in urinary MCP1/uCr and/or urinary TIMP1/uCr biomarker levels.

## 2. Inclusion of additional safety endpoints

Additional safety endpoints were added to the analysis that were not described in the protocol: AEs leading to premature discontinuation of study medication, proportion of participants with temperature ≥38.5°C (indicating fever), and proportion of participants with new or worsening edema compared to baseline. They are standard safety parameters in this population.

Protocol: None

**SAP**: Section 4.2. Secondary Endpoints.

- 3. Incidence of adverse events leading to premature discontinuation of study medication, defined as the proportion of participants with treatment-emergent adverse events and the number of treatment-emergent adverse events that led to premature discontinuation of study medication, overall, by system organ classification, by relatedness to study medication, and by severity
- 4. Proportion of participants with abnormal laboratory tests for ALT, AST, total bilirubin, hemoglobin, hematocrit, and platelet count, proportion of participants with temperature ≥38.5°C (indicating fever), and proportion of participants with new or worsening edema (over all body locations and by each location) over the course of the 10-week intervention period compared to baseline

#### 3. Clarification of exploratory endpoints

The protocol included time to reduction in the two biomarkers, urinary MCP1/uCr and urinary TIMP1/uCr. The SAP clarifies that the trajectory of the biomarkers over the course of the study will provide the evaluation of the time to reduction.

Protocol: Section 4.2.3 EXPLORATORY ENDPOINTS.

Time to reduction of urinary MCP1/uCr and urinary TIMP1/uCr biomarkers from baseline

#### SAP: Section 4.3

- 2. Change from baseline to weeks 2, 4, and 8 in MCP1/uCr
- 3. Change from baseline to weeks 2, 4, and 8 in TIMP1/uCr
- 4. Percent change from baseline to weeks 2, 4, 8 and 10 in urinary MCP1/uCr
- 5. Percent change from baseline to weeks 2, 4, 8 and 10 in urinary TIMP1/uCr
- 6. Urinary MCP1/uCr values at baseline and weeks 2, 4, 8 and 10
- 7. Urinary TIMP1/uCr values at baseline and weeks 2, 4, 8 and 10
- 9. Correlation coefficient between uEGF/uCr at baseline with changes and percent changes in urinary MCP1/uCr and urinary TIMP1/uCr biomarker levels and in eGFR and UPCR values at week 10.

## 4. Change in analysis of the primary endpoints

The nonparametric approach was considered more appropriate for the small sample size.

Protocol: Section 10.3.2 ANALYSIS OF THE PRIMARY EFFICACY ENDPOINT(S).

The changes from baseline to week 10 in urinary MCP1/uCr and TIMP1/uCr levels will be tested using the paired t-test or Wilcoxon signed-rank test (if distributional assumptions are not met).

**SAP:** Section 9.1 Analyses of Primary Endpoints.

The changes from baseline to week 10 in urinary MCP1/uCr and urinary TIMP1/uCr levels will be tested using the Wilcoxon signed-rank test.

# 12. List of Tables, Listings and Figures

All tables, listings and figures are saved in a separate file as supplementary material.

#### 12.1 List of Tables

- Table 1. Subject Disposition Summary. All Subjects.
- Table 2. Reasons for Early Study Discontinuation. All Subjects.
- Table 3. Duration of Follow-Up Period. All Subjects.
- Table 4. Number of Enrolled Subjects by Site. All Subjects.
- Table 5. Proportion of Participants Receiving 1, 2, 3, 4 and 5 (all) Doses of Adalimumab. As-Treated Population.

- Table 6. Duration of Adherence to Study Medication Summary. As-Treated Population
- Table 7. Demographic and Baseline Characteristics. As-Treated Population.
- Table 8. Change in urinary MCP1/uCr levels from Baseline to Week 10. As-Treated Population.
- Table 9. Change in urinary TIMP1/uCr levels from Baseline to Week 10. As-Treated Population.
- Table 10.1. Treatment-Emergent Serious Adverse Event (SAE) Summary. As-Treated Population.
- Table 10.2. Treatment-Emergent Serious Adverse Event (SAE) by System Organ Class and by Severity. As-Treated Population.
- Table 10.3. Treatment-Emergent Serious Adverse Events (SAE) by System Organ Class and by Relatedness to Study Medication. As-Treated Population.
- Table 11.1. Non-Serious Treatment-Emergent Adverse Event (AE) Summary. As-Treated Population.
- Table 11.2. Non-Serious Treatment-Emergent Adverse Events (AE) by System Organ Class and by Severity. As-Treated Population.
- Table 11.3. Non-Serious Treatment-Emergent Adverse Events (AE) by System Organ Class and by Relatedness to Study Medication. As-Treated Population.
- Table 12.1. Treatment-Emergent Adverse Events Leading to Premature Discontinuation of Study Medication Summary. As-Treated Population.
- Table 12.2. Treatment-Emergent Adverse Events Leading to Premature Discontinuation of Study Medication by System Organ Class and by Severity. As-Treated Population.
- Table 12.3. Non-Serious Treatment-Emergent Adverse Events Leading to Premature Discontinuation of Study Medication by System Organ Class and by Relatedness to Study Medication. As-Treated Population.
- Table 13. Proportion of participants with temperature ≥38.5°C (indicating fever). As-Treated Population.
- Table 14. Proportion of participants with new or worsening edema (over all body locations and by each location) over the course of the 10-week intervention period compared to baseline. As-Treated Population.
- Table 15. Percent change in eGFR from baseline to week 10. As-Treated Population.
- Table 16. Percent change in UPCR from baseline to week 10. As-Treated Population.
- Table 17. Proportion of participants achieving a nadir UPCR <1.5 g/g and at least a 40% reduction from baseline at week 10. As-Treated Population.
- Table 18.1. Proportion of Participants with Abnormal Laboratory Tests for ALT, AST, Total Bilirubin, Hemoglobin, Hematocrit, and Platelet Count Over the Course of the 10-Week Intervention Period. As-Treated Population.
- Table 18.2. Shift Table for Normal and Abnormal Laboratory Test Changes from Screening to Weeks 0, 2, 8, 10, and 14 in ALT, AST, Total Bilirubin, Hemoglobin, Hematocrit, and Platelet Count. As-Treated Population.
- Table 19. Correlations between TNF activation score and urinary MCP1/uCr and TIMP1/uCr biomarker levels at baseline. As-Treated Population with Kidney Biopsy Tissue Collected within 12 Months of Study Baseline.

- Table 20.1. Change from baseline to weeks 2, 4, and 8 in urinary MCP1/uCr. As-Treated Population.
- Table 20.2. Percent change from baseline to weeks 2, 4, 8, and 10 in urinary MCP1/uCr. As-Treated Population.
- Table 20.3. Urinary MCP1/uCr values at baseline and weeks 2, 4, 8, and 10. As-Treated Population.
- Table 21.1. Change from baseline to weeks 2, 4, and 8 in urinary TIMP1/uCr. As-Treated Population.
- Table 21.2. Percent change from baseline to weeks 2, 4, 8, and 10 in urinary TIMP1/uCr. As-Treated Population.
- Table 21.3. Urinary TIMP1/uCr values at baseline and weeks 2, 4, 8, and 10. As-Treated Population.
- Table 22. Change in uEGF/uCr levels from baseline to weeks 2, 4, 8, and 10. As-Treated Population.
- Table 23. Correlation coefficient between uEGF/uCr at baseline with changes and percent changes in urinary MCP1/uCr and urinary TIMP1/uCr biomarker levels and in eGFR and UPCR values at week 10. As-Treated Population.
- Table 24. Changes in FSGS-MCD Patient Reported Outcome (PRO) score from baseline to weeks 2, 4, 8 and 10. As-Treated Population.

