2.2 RATIONALE

Based on molecular profiling, informed therapy selection targeting the underlying disturbance has been used successfully in health care and biomedical research. When successful, this forms the basis of precision medicine for the treatment of selected patient populations.

The Nephrotic Syndrome Study Network (NEPTUNE, PI [name]) study investigators have used genome wide expression profiles of renal biopsy specimens available from more than 250 patients to identify molecular subgroups of NS². Three distinct patient subgroups were identified and associated with long-term outcomes. Molecular pathway analysis of the subgroups with TR-MCD and FSGS showed activation of TNF as defined by causal inference network analysis of established downstream pathway members, including TIMP1 and MCP1 in one of the 3 subgroups. These patients presented with higher levels of proteinuria, lower levels of GFR, and more rapid progression of their glomerular disease. A TNF Z-score was computed for each NEPTUNE participant with MCD and FSGS. The score is the average Z-score of gene expression level across 145 TNF pathway genes from the tubulointerstitial compartment

of each participant's renal biopsy. Urinary MCP1 and TIMP1 were measured by ELISA from their baseline study visit and normalized to urine creatinine. Correlations of TNF gene expression Z-score with urinary biomarkers are shown in Figure 1 and distributions of these measures in boxplots from TNF z-score < 0 vs > 0 are plotted in Figure 2.

Figure 2: Scatter plot of TNF z- score and urinary TIMP1/Cr, A: All FSGS and MCD patients (corr = 0.47, P<0.001) TNF z-score and urinary MCP1/Cr, B: All FSGS and MCD patients (corr = 0.51, P<0.001) TNF z-score and urinary TIMP1/Cr ng/mg. (L. Mariani, et al 2017)

[figure not shown]
[figure not shown]

Figure 3: Distribution of biomarker level by TNF Z-score category. Difference in means was statistically significant (TIMP1, p-value 0.009; MCP1 p-value 0.001) (L. Mariani, et al 2017)

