5.3 STRATEGIES FOR RECRUITMENT AND RETENTION

Patients will be recruited from the active population of patients with FSGS or TR-MCD w at participating sites. TR-MCD is defined as persistent proteinuria despite treatment. Following informed consent and when appropriate, assent, a screening visit will be conducted. Patients with elevated TIMP1/Cr and MCP1/Cr levels and meeting all other eligibility criteria will be scheduled to receive adalimumab every two weeks for 8 weeks (5 total doses). It is anticipated that only 25% of screened patients will be eligible for study participation based on TIMP1/Cr and MCP1/Cr levels. Eight eligible patients will begin study intervention with a goal to have a minimum of 6 patients fully completing the intervention phase and therefore contributing to the final analysis of the primary endpoint after 5 doses of adalimumab over an 8 week period.

Patients will be compensated for study participation to offset costs related to travel to study visits and incidentals.

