7.2.1 SCREENING VISIT

The screening visit will take place preferably within 2 weeks, but no more than 6 weeks prior to the baseline visit (Week 0)

At the screening visit:

- Patient/Parent provides written informed consent and HIPAA authorization prior to any evaluation or testing. Minor participants should provide assent in accordance with IRB guidelines
- b. A review of existing medical records and tests, provided by the patient or referring physician, will be performed to document the history of FSGS or TR-MCD and general medical history.
- c. Vital signs including height, weight, temperature and blood pressure are obtained.
- d. The patient undergoes a physical examination.
- e. The patient has blood and spot urine collected for monitoring labs, including urine pregnancy test (if applicable).
- f. A spot urine sample is obtained for measurement of target engagement biomarkers
- g. If the patient consents, biorepository samples should be obtained
- h. Archived kidney biopsy tissue is requested to be sent [when available and if not already submitted to the NEPTUNE study] to the laboratory at the University of Michigan for gene expression profiling for mechanisms of disease
- i. Archived kidney biopsy report is anonymized and uploaded into the study electronic data capture system for central review

At Screening, a preliminary evaluation is performed and once screening is complete, if all inclusion and no exclusion criteria are met, the patient is deemed eligible and will be asked to return for the baseline visit for study drug initiation. Subjects who have not met study enrollment criteria will be considered a screen failure and their study participation will end.

Repeat Screening. If the patient is found to be ineligible, a repeat screening visit may be performed at the local clinician investigator's discretion.

Once eligibility is confirmed, the patient should be instructed to bring a 24-hour urine specimen to the baseline visit.

7.2.2 BASELINE/WEEK 0

The Baseline visit/Week 0 will occur within 6 weeks of the screening evaluation. The following procedures will take place at the baseline visit:

- a) Interval medical history
- b) Review of concomitant medications
- c) Physical examination
- d) Assessment of adverse events
- e) Vital signs will be obtained including weight, blood pressure, and temperature
- f) Subject to complete HRQOL assessment

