### 4.3 Exploratory Endpoints

- 1. In the subgroup of participants with kidney biopsy tissue collected within 12 months of study baseline, correlation coefficient between intra-renal gene expression of TNF (TNF activation score) [1] and urinary MCP1/uCr and TIMP1/uCr biomarker levels at baseline
- 2. Change from baseline to weeks 2, 4, and 8 in urinary MCP1/uCr
- Change from baseline to weeks 2, 4, and 8 in urinary TIMP1/uCr
- 4. Percent change from baseline to weeks 2, 4, 8, and 10 in urinary MCP1/uCr
- 5. Percent change from baseline to weeks 2, 4, 8, and 10 in urinary TIMP1/uCr
- 6. Urinary MCP1/uCr values at baseline and weeks 2, 4, 8, and 10
- 7. Urinary TIMP1/uCr values at baseline and weeks 2, 4, 8, and 10
- 8. Changes in urinary epidermal growth factor normalized to urinary creatinine (uEGF/uCr) biomarker levels from baseline to week 10
- 9. Correlation coefficient between uEGF/uCr at baseline with changes and percent changes in urinary MCP1/uCr and urinary TIMP1/uCr biomarker levels and in eGFR and UPCR values at week 10.
- Changes in FSGS-MCD Patient Reported Outcome (PRO) score from baseline to weeks 2,
   4, 8 and 10

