## 7.2 Analysis Dataset

All eligible participants who received at least one dose of adalimumab (as-treated population) are analyzed for primary, secondary, and exploratory endpoints.

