## 9.4 Exploratory Analyses

Spearman correlations and scatterplots are provided to assess the correlation of TNF activation score and urinary MCP1/uCr and urinary TIMP1/uCr biomarker levels at baseline, and the correlation of uEGF/uCr at baseline with changes and percent changes in urinary MCP1/uCr and urinary TIMP1/uCr biomarker levels and in eGFR and UPCR values at week 10.

Continuous outcomes (e.g., eGFR, uEGF/uCr biomarker levels) will be summarized descriptively, including baseline, follow-up and changes from baseline and graphically as spaghetti plots of participants' changes (absolute and relative) over time and values over time.

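### SAP Table 19 correlates tissue TNF activation with urinary MCP1/uCr and TIMP1/uCr only in patients selected on those markers, which biases the coefficient downward and is not flagged

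*SAP*

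**What the plan says.** SAP 4.3 item 1 defines the endpoint "In the subgroup of participants with kidney biopsy tissue collected within 12 months of study baseline". SAP 9.4 gives the method: "Spearman correlations and scatterplots are provided to assess the correlation of TNF activation score" and the two urinary markers at baseline. SAP 7.2 sets the population: "All eligible participants who received at least one dose of adalimumab (as-treated population) are analyzed for primary, secondary, and exploratory endpoints". Table 19 repeats this as the "As-Treated Population with Kidney Biopsy Tissue Collected within 12 Months of Study Baseline", and Figures 7.1-7.2 are also as-treated.

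Treatment depended on the same markers. Protocol 2.2 admits patients whose predicted probability of a positive TNF Z-score is at least 50%, from a logistic score in log2 TIMP1/Cr and log2 MCP1/Cr. Protocol 5.3 adds: "It is anticipated that only 25% of screened patients will be eligible for study participation based on TIMP1/Cr and MCP1/Cr levels".

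Urine for the markers is taken at screening. At the same visit, under Protocol 7.2.1, "Archived kidney biopsy tissue is requested to be sent [when available and if not already submitted to the NEPTUNE study". Both steps come before eligibility is settled, yet no planned analysis uses data from patients who fail screening.

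The unselected reference values, in Protocol 2.2, are 0.47 (TIMP1/Cr) and 0.51 (MCP1/Cr) in the NEPTUNE FSGS and MCD patients. These follow the order of the figure caption, whose labels are not fully clear.

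**The concern.** A correlation estimated where one variable has been cut to its upper part is smaller than the correlation in the whole population. Here the cut falls on a combination of the two markers being correlated, and patients with low scores are absent by design.

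SAP section 10, change 1, drops the hypothesis that urine and tissue profiling can identify patients with TNF up-regulation. Table 19 is then the only planned comparison of urine with tissue inside the trial. The endpoint rationale in SAP 4.3 still rests on baseline marker levels reflecting TNF activity in the kidney. An unlabelled low or negative coefficient could be set beside 0.47 and 0.51 and taken as evidence against that link, when part of the gap is produced by the entry rule.

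**Working it through.** **Inputs from the documents**

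- Unselected correlations: TIMP1 0.47, MCP1 0.51 (Protocol 2.2). They cannot be reproduced without patient data. The documents give no post-selection value.
- Fraction selected: 25% (Protocol 5.3). Model 3 in Protocol 2.2 implies 8/49 = 16.3%. With 49 patients and 13 events, 6 true and 2 false positives give PPV 6/8 = 75% and (6 + 34)/49 = 82% correct.
- Score weights: the regression output in Protocol 2.2 gives MCP1 0.59214 and TIMP1 0.4325066. The equation printed below it attaches them the other way round. Both versions were run.
- At most 8 treated patients, fewer with recent tissue.

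**Assumptions (not in the documents)**

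Joint normality on the log scale; NEPTUNE correlations hold in the screened population; inter-marker correlation about 0.3-0.7; correlation t between screening and week 0 values of 1.0, 0.8 or 0.6.

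**Formula**

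For tissue score Z, marker X and selection score S:

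r' = (r − K·r_ZS·r_XS) / √[(1 − K·r_ZS²)(1 − K·r_XS²)]

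K is the variance lost by truncating a normal variable. For the top 25% the cut is 0.6745 and the mean above it is 1.2711, so K = 1.2711 × (1.2711 − 0.6745) = 0.758.

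**Worked case: MCP1, regression-output weights, equal SDs, inter-marker correlation 0.5, top 25%, t = 1**

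- SD of S = √(0.3506 + 0.1871 + 0.2561) = 0.891
- r_XS = (0.5921 + 0.5 × 0.4325)/0.891 = 0.907
- r_ZS = (0.5921 × 0.51 + 0.4325 × 0.47)/0.891 = 0.567
- r' = (0.51 − 0.758 × 0.567 × 0.907)/√(0.756 × 0.376) = 0.120/0.533 = 0.225
- Fraction kept: 0.225/0.51 = 0.44

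The same steps for TIMP1 (r_XS = 0.818) give 0.118/0.610 = 0.194, and 0.194/0.47 = 0.41.

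**Selection on screening urine, correlation on week 0 urine**

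With t below 1, r_XS becomes t × 0.907. The answer also depends on whether screening urine tracks tissue as well as week 0 urine does (r_ZS stays 0.567) or only through week 0 (r_ZS becomes t × 0.567).

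| t | r', screening tracks tissue equally | Fraction kept | r', screening tracks tissue only through week 0 | Fraction kept |
|---|---|---|---|---|
| 1.0 | 0.225 | 0.44 | 0.225 | 0.44 |
| 0.8 | 0.198/0.674 = 0.294 | 0.58 | 0.260/0.712 = 0.366 | 0.72 |
| 0.6 | 0.276/0.766 = 0.360 | 0.71 | 0.370/0.841 = 0.439 | 0.86 |

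**Across both markers, both selected fractions and both sets of weights**

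- t = 1.0: about 0.2-0.5
- t = 0.8: about 0.5-0.7
- t = 0.6: about 0.65-0.85

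If the two markers were uncorrelated and the printed equation was applied, the extremes widen to 0.03 (TIMP1, t = 1, top 16.3%) and 0.92 (MCP1, t = 0.6). Spearman ratios run a few hundredths lower at t = 1: 0.48 and 0.35, against 0.50 and 0.38, with inter-marker correlation 0.64 and SDs inferred from the odds ratios and c-statistics.

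**Chance of a zero or negative MCP1 Spearman coefficient (simulation)**

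- n = 8, no selection: about 10%
- n = 8, top 25%, regression-output weights: about 16-34% over the t range
- n = 4, no selection: about 24%

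**Sampling error at this size**

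At n = 8 with no selection, a true r of 0.51 has an approximate 95% interval of −0.30 to 0.89. At 25% eligibility, 8 treated implies 8/0.25 = 32 screened. If all 32 had tissue, the interval would be 0.20 to 0.73.

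**The case against.** The endpoint is exploratory, the analyses are mainly descriptive, and no decision is tied to Table 19. The SAP plans no comparison with 0.47 or 0.51. With at most 8 patients, sampling error is large whatever the population. All of this stands, and it keeps the point minor.

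A reader might infer that selection cuts the correlation to less than half. The documents do not support that as a fact. It needs the selecting and analysed values to be nearly the same, but selection uses screening urine and the correlation uses week 0 urine, which Protocol 7.2.1 allows to be up to 6 weeks later. Even with identical values, MCP1 is borderline: truncating directly on it at the top 25% keeps 0.28/0.51 = 0.55.

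A reader might also set the risk of a wrong sign in 4-8 selected patients against that in 12-32 unselected ones. That mixes selection with sample size. The fair comparison holds n at 8.

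Nor do the documents show that the SAP discards complete data. Tissue comes only when available, SAP 6.4 keeps only biopsies within a year of consent, participation ends at screen failure, and nothing says that screen failures' tissue was profiled. It is also inexact that each patient was high on both markers: the inclusion criterion reads and/or, and the working rule is a composite.

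What remains is that the direction of the bias is known, the plan is silent on it, and labelling it costs almost nothing.

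**Conclusion.** The point holds as a downward bias of uncertain size. Restricting Table 19 and Figures 7.1-7.2 to treated patients leaves roughly 0.2-0.85 of the unselected correlation. The range reflects the screening-to-week-0 correlation (1.0 to 0.6), the inter-marker correlation, the selected fraction and which version of the weights was applied. With 8 patients, it takes the chance of a zero or negative MCP1 coefficient from about 10% to about 16-34%. The rest of the imprecision is due to the number of patients.

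The result rests on normality and on the NEPTUNE correlations carrying over to the screened population. The documents do not support the stronger conclusion that the as-treated analysis should be replaced. Screen failures' scores may not exist, week 0 values would give way to screening values, and assay plates may differ. This is a minor improvement to an exploratory analysis.

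**What to change.** - Keep the as-treated week 0 correlation. Label it in Table 19 and Figures 7.1-7.2 as selected on the urinary biomarkers, attenuated by range restriction, and not comparable with the unselected NEPTUNE values.
- Add a second row to Table 19 for all screened participants, treated or not, who already have a TNF activation score from tissue within 12 months and a screening urine sample. Use screening MCP1/uCr and TIMP1/uCr, and report n. Screen failures have no baseline visit, so count the 12 months from consent, as SAP 6.4 does. Carry the wording into SAP 4.3 item 1, 7.2 and 9.4.
- Footnote the limits: the number of screen failures with a score is unknown and may be small; screening assays may have been run on different plates from the shared plate described in SAP 6.4; NEPTUNE participants may overlap the sample that produced 0.47 and 0.51.
- Reconcile the regression output and the printed equation in Protocol 2.2, and state which was applied.

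The cost is SAP wording, a label and one table row. It needs no new tissue, profiling or visits. If no screen failure has a score, the label alone is enough.
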